## 8.5. Health Economic Analysis

The analytical approach will be a cost-efficacy analysis. This approach combines measures of costs over time with efficacy measures.

### Resource Utilisation and Costs

The analysis of medical consumption will be performed by comparing the number of resources consumed per treatment group. Health care resource consumption will be expressed in units for each selected resource (e.g. number of days of hospitalisation, the number of physicians' consultations). For each selected resource unit, both the frequency of use (i.e., % patient usage) and intensity of use (i.e., the average amount used) will be presented. The costs by treatment group will be presented in an aggregate manner and by subgroups.

The pooling of resource utilisation patterns will be undertaken unless any country effect or country × treatment interaction effect has been noted in the primary efficacy criteria.

### Cost Estimates

The resource consumption will be valued by country, using average national charges/costs collected outside the clinical study by resource items; detailed valuation methods will be country-specific.

### Efficacy

Efficacy criteria, as defined in Section 3.5. Study endpoints will be compared across groups.

### Cost-efficacy Analysis

The incremental cost-efficacy ratio will be calculated in case a difference in efficacy is found between groups and if the costs in the Akynezo® group are higher. If that is not the case, then incremental costs (or savings) results across groups will be presented as cost-minimisation or cost-consequence results.

The different options are summarised in Table 1.

CONFIDENTIAL

Confidential	MyRisk	Date: 05 February 2024
	Protocol	
	PROTOCOL NUMBER: IBA1160	Version: 5.1

Table 1: Cost-Efficacy Analysis

	Difference in Efficacy	No difference in Efficacy
Akynzeo® group costs lower	Savings	Savings
Akynzeo® group costs higher	Cost-efficacy	Incremental Costs

All resource consumption data analysis will be specified in a separate Health Economics Analysis Plan.

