9.6.3. Cost-efficacy Analysis

The economic data will be collected primarily in physical units of health care resource used per patient and per event (efficacy / safety).

The incremental cost-efficacy ratio (ICER) is defined as the difference in cost between the study arms, divided by the difference in efficacy. It will be calculated in case a difference in efficacy is found between groups and if the costs in the Akynzeo group are higher. If that is not the case, then incremental costs (or savings) results across groups will be presented as cost-minimisation or cost-consequence results.

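### The ICER trigger and Protocol Table 1 ignore the direction of the efficacy difference and leave the trigger undefined, so the health economic objective can receive a misleading answer

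*Protocol*

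**What the plan says.** Protocol 8.5 (Cost-efficacy Analysis) and SAP 9.6.3 set the same two conditions for an incremental cost-efficacy ratio (ICER). The protocol gives the efficacy condition as "The incremental cost-efficacy ratio will be calculated in case a difference in efficacy is found between groups" and adds the cost condition in the same sentence. In the SAP's words: "It will be calculated in case a difference in efficacy is found between groups and if the costs in the Akynzeo group are higher". If either condition fails, "then incremental costs (or savings) results across groups will be presented as cost-minimisation or cost-consequence results". Nothing says which of the two presentations applies when.

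The SAP gives the formula: "The incremental cost-efficacy ratio (ICER) is defined as the difference in cost between the study arms, divided by the difference in efficacy". It gives no interval or resampling method for the ratio. On the effect side, Protocol 8.5 (Efficacy) says only: "Efficacy criteria, as defined in Section 3.5. Study endpoints will be compared across groups". Section 3.5 lists many endpoints, and none is named as the denominator.

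Table 1, which is in the protocol only, crosses two cost rows with two efficacy columns (difference, no difference). The row "Akynzeo® group costs lower" reads *Savings* in both columns. The row "Akynzeo® group costs higher" reads *Cost-efficacy* under difference and *Incremental Costs* under no difference. Directly after the table the protocol adds: "All resource consumption data analysis will be specified in a separate Health Economics Analysis Plan". That plan is not among the documents.

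**The concern.** Two features of the rule can mislead.

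- **Direction.** A difference in efficacy can favour either arm, and the primary test is two-sided. A table that records only whether a difference exists cannot tell a good result from a bad one.
- **The trigger.** The ratio depends on a difference being found, but the test, threshold and endpoint are not given. If failure to find a difference is treated as no difference, a superiority trial that misses its target can be reported on costs alone, as though equal efficacy had been shown. Cost-minimisation is appropriate only when effects can be taken as equal.

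At stake is objective 6 (resource utilisation and health economic outcome): a real benefit could be left out of the economic summary, or a loss of efficacy could carry a favourable label.

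**Working it through.** **Step 1. Fill in Table 1 by direction.** This needs no assumption. Two cost results and three efficacy results give six outcomes; the table has four cells.

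| Akynzeo cost | Akynzeo efficacy | Label in Table 1 | What the outcome is |
|---|---|---|---|
| Lower | Better | *Savings* | Akynzeo dominates |
| Lower | No difference | *Savings* | Saving, if effects really are equal |
| Lower | Worse | *Savings* | Trade-off: money saved, responses lost |
| Higher | Better | *Cost-efficacy* | Trade-off: the ICER is informative |
| Higher | No difference | *Incremental Costs* | Extra cost, if effects really are equal |
| Higher | Worse | *Cost-efficacy* | Akynzeo is dominated |

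The third and sixth rows are mislabelled. In the sixth, both conditions for the ratio are met, so it would be computed: a positive cost difference over a negative efficacy difference gives a negative ICER. In the first and third, the cost condition fails, so the text allows a cost-minimisation presentation even though a difference in efficacy has been found.

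**Step 2. Reproduce the planned power.** Inputs from Protocol 8.2 and SAP 9.2: 71% v 60%, two-sided 0.05, 80% power, 1:1, three cycles, correlation 0.5, missing 0%, 7.5% and 15%, independent method.

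- Observation probabilities: 1, 0.925, 0.85; sum 2.775.
- f = [2.775 + 2 × 0.5 × (1×0.925 + 1×0.85 + 0.925×0.85)] / 2.775² = 5.336 / 7.701 = 0.693.
- Log-odds difference: ln(0.71/0.29) − ln(0.60/0.40) = 0.895 − 0.405 = 0.490.
- n per arm = [1/(0.71×0.29) + 1/(0.60×0.40)] × 0.693 × (1.960 + 0.842)² / 0.490² = 204.5, so 205 per arm and N = 410.
- Power at 205 per arm is 80.1%. The plan's figure reproduces.

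**Step 3. How often the *No difference* column is reached.** Assumption, not in the documents: a found difference means two-sided p<0.05 on the primary endpoint. On the log-odds scale the chance at the planned effect is 1 − 0.801 = 0.199. On the risk-difference scale, with control response 60%:

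- SE = √{[0.60×0.40 + p(1−p)] × 0.693 / 205}, where p is the true Akynzeo response. At p = 0.71 this is √(0.4459 × 0.693 / 205) = 0.0388.
- The chance of no significant difference in Akynzeo's favour is Φ(1.96 − difference/SE). At these three values the chance of a significant adverse result is negligible.

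| True difference | SE | Chance of *No difference* |
|---|---|---|
| +11 points | 0.0388 | 19% |
| +8 points | 0.0393 | 47% |
| +5.5 points | 0.0397 | 72% |

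The largest observed difference still classed as no difference is about 1.96 × 0.0388 = 0.076, or 7.6 points. At that value the ICER would be 1/0.076 ≈ 13.1 times the incremental cost per extra per-cycle response (1/0.11 ≈ 9.1 times at 11 points), but it would not be reported.

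**Step 4. How often a significant adverse result arises.** Same assumption: Φ(−1.96 − difference/SE) gives 2.5% at a true difference of zero, 11% at −3 points and 27% at −5.5 points. Whether it is then labelled *Savings* or *Cost-efficacy* depends on costs, for which the documents give no figures.

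**The case against.** The strongest reply has four parts.

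- **Efficacy is not removed.** A reader might infer that, without a found difference, efficacy drops out of the economic result. The documents do not support that. The fallback includes cost-consequence, which can show effects beside costs; Protocol 8.5 compares the efficacy criteria across groups without condition; and complete response is tabulated in any case (SAP 10.1, Table 14.2-1). An adverse efficacy result would therefore be visible elsewhere and not concealed. This stands, and it is why the rule *can* mislead and does not necessarily do so. It does not repair the Table 1 labels or supply a rule for choosing the presentation.
- **Significance is not mentioned.** A reader might infer that a non-significant result is formally treated as equal efficacy. Neither document ties the trigger to a p-value. This stands: the firm defect is that the term is undefined, and the percentages in Steps 3 and 4 are conditional.
- **A separate plan exists.** One cannot say that no joint uncertainty of cost and effect is planned, only that these two documents describe none. The SAP output list has resource-use tables but no cost or ICER table, so those outputs may be specified elsewhere. The deferral, however, is for resource-consumption data. The ICER trigger is fixed in both documents and the labels are fixed in the protocol.
- **The table is not in the SAP.** True. The conditions and the fallback are in both documents; the labels need a protocol change.

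**Conclusion.** The point holds in a limited form. With no assumption, Protocol Table 1 misclassifies two of the six possible outcomes, both with Akynzeo less effective, and the choice between cost-minimisation and cost-consequence is left open. The trigger and the ICER efficacy measure are undefined. If the trigger means two-sided p<0.05 on the primary endpoint, the planned 11-point benefit would fall under *No difference* in about one trial in five, and a benefit half that size in about 72%. Without cost data, the size of any economic error cannot be given.

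The stronger statement, that the rule gives a wrong economic conclusion, is not supported, because efficacy is compared and reported in any case. This is a minor point on one secondary objective. The primary efficacy analysis and its sample size are unaffected.

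**What to change.** - In Protocol Table 1, split the difference column into Akynzeo better and Akynzeo worse. Label lower cost with worse efficacy as a trade-off, and higher cost with worse efficacy as Akynzeo dominated.
- In Protocol 8.5 and SAP 9.6.3, name the efficacy measure for the ICER, for example overall-phase complete response.
- In the same two places, always report incremental cost and incremental effect with their joint uncertainty, for example a bootstrap cost-effectiveness plane or net benefit, whatever the efficacy p-value or the sign of the cost difference. The undefined trigger then no longer decides what is shown.
- Align the separate Health Economics Analysis Plan with this wording.

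The cost is a short text change in both documents and a little more analysis, with no new trial data. The headline labels become less simple. Making the change before database lock avoids choosing the economic presentation after the results are known.

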## 9. Confidentiality

The data collected within the database will be pseudonymised.

Each patient will be enrolled in the study electronic database under a unique Identification Number (ID) and henceforth will be identifiable only via this ID code. Re-identification of patients from the patient number in the study will not be possible. The unique ID of the individual patient is only known to collaborating physician or qualified medical personnel involved in the project.

In order to respect patient privacy, all patient records, study reports, and communications will identify the patient by the assigned unique patient number. The patient's confidentiality will be maintained and will not be made publicly available, to the extent permitted by the applicable laws and regulations. The study sponsor of this study is the owner of all data and any information or material collected in the database.

### 9.1. Personal Data Protection

The processing of personal data of natural persons involved in the study is carried out in accordance with any applicable "Data Protection Laws", including without limitation the Regulation (EU) 2016/679 of the European Parliament and of the Council on the protection of natural persons with regard to the processing of personal data and on the free movement of such data (hereinafter „GDPR”), as well as any country legislation in relation to the protection of personal data. Both the controller and the processor are obliged to observe the rules and obligations coming from the applicable Data Protection Laws, as well as to set up the relevant processes for data subjects' rights fulfilment.

Whether personal/pseudonymous or anonymous data is processed within the study, it is always protected information processing. Therefore, IBA has established the ISMS Information Security Management System in compliance with the standard ISO/IEC 27000. By this way IBA has accepted and implemented appropriate technical and organisational security measures required by standard and Regulation.

#### 9.1.1. Patients' Personal Data Processing

The controller of personal data, who determines the purposes and means of processing within the overall study is the Sponsor (Helsinn Healthcare SA, [name]). The patient can't be included in the study without signed **explicit informed consent**. The responsible for acquiring and storing of patient informed consent for statistical and scientific purposes is the investigator/Provider of health services (site) according to conditions stated in the contract with the participating site. The specific

CONFIDENTIAL

Confidential	MyRisk	Date: 05 February 2024
	Protocol	
	PROTOCOL NUMBER: IBA1160	Version: 5.1

purposes are described in the informed consent form. Information that the patient gave the consent with processing of his/her data should be confirmed in the EDC system. Without this confirmation, the new patient can't be entered.

The processing of identifiable personal data of the patient in the study, before pseudonymisation, is allowed only to an investigator/ Provider of health services (site). The investigator/Provider of health services (site) shall enter the patient's data into the EDC system under a unique ID, the investigator is the only person who can identify the patient based on his/her ID. Other persons accessing the study are unable to identify a patient in the EDC system. The physician is the contact person for the patient's rights fulfillment. The physician shall be familiarized with rules for personal data processing.

Further data processing in the study is in the pseudonymous regime, where the persons accessing the registry based on their access rights are unable to identify the patient (directly or indirectly).

### 9.1.2. Investigators' Personal Data Processing

Within the study, the personal data of cooperating investigators are processed by IBA on the base of the creation of access accounts and communication during the study course. On the base of the legitimate purpose of the controller, the investigator's data might be communicated to, and processed by, the controller as a processor to ensure the smooth running of the study and high quality of collected data.

Should the Sponsor receive any information on investigators, the Controller of investigators personal data is Helsinn. The processors are IBA, local CROs and permitted sub-processors managing the investigators for the study.

In such a case, the investigators are properly informed about their data processing; IBA, local CROs and permitted sub-processors to undertake to provide adequate notices to the investigator (in a form provided by and on behalf of the Sponsor) and undertake to ensure that all investigators have acknowledged to the processing of their personal data as required for the following purposes: (a) the conduct of the Study; (b) review by governmental or regulatory agencies, public authorities or pharmaceutical industries associations, IBA, the Sponsor, and their agents and affiliates; and (c) compliance with legal or regulatory requirements including those on disclosure of transfers of values from pharmaceutical companies to healthcare professionals and healthcare organizations; and (d) storage in databases for use in selecting investigators, study staff, and institutions for future clinical trials.

### 9.1.3. Ensuring of Personal Data Protection

IBA has implemented the following measures in compliance with the ethical and legal requirements to ensure the maximal possible safety of collected data:

- Technical measures of EDC system
- Internal standards form personal data processing, risks management, incident management, training system
- Access policy – access to the data only for the authorized person on the base of their access rights
- Training of investigators

CONFIDENTIAL

Confidential	MyRisk	Date: 05 February 2024
	Protocol	
	PROTOCOL NUMBER: IBA1160	Version: 5.1

#### 9.1.4. Description of Archiving and Disposal of Data after Finishing the Study

Unless prohibited law or otherwise required by the applicable law to be preserved, IBA will securely delete all personal data in its possession or under its control upon the termination of the study according to the requirements of the Data Protection Laws, with the exception of personal data that in accordance with the applicable laws, regulations and/or guidelines in force must be conserved by the IBA.

## 10. Safety Management

All Adverse Events (AEs) occurring after signing the informed consent through the AE reporting period are to be recorded on the AE pages of the eCRF irrespective of its relatedness to the study drug.

### 10.1. Definitions

An AE is any untoward medical occurrence in a patient or clinical investigation subject administered a pharmaceutical product and which does not necessarily have to have a causal relationship with this treatment. An AE can therefore be any unfavorable and unintended sign (including an abnormal laboratory finding), symptom, or disease temporally associated with the use of a medicinal investigational products, whether or not considered related to the medicinal investigational products.

AEs include the following types of occurrences:

- Other medical experiences, regardless of their relationship to the study drug, such as injury, surgery, accidents, increased severity of pre-existing symptoms, apparently unrelated illnesses, and significant abnormalities in clinical laboratory values, physiological testing, or physical examination findings;
- Reactions from drug overdose, abuse, misuse, medication errors, withdrawal, hypersensitivity, or toxicity;
- Clinically relevant abnormal findings, including laboratory abnormalities, as well as worsening of any pre-existing condition at each visit;
- Adverse drug reactions.

Planned surgical interventions or planned hospitalizations scheduled prior to the informed consent but performed during the study (e.g. corrective procedures, biopsy, additional chemotherapy cycles, etc.) should NOT be considered AEs.

An Adverse Drug Reaction (ADR) is any noxious and unintended response associated with the investigational medicinal product at any dose. Response in this context means that a causal relationship between a medicinal product and an AE is at least a reasonable possibility.

CONFIDENTIAL

Confidential	MyRisk	Date: 05 February 2024
	Protocol	
	PROTOCOL NUMBER: IBA1160	Version: 5.1

A Serious Adverse Event (SAE) is any event that suggests a significant hazard, contraindication, side effect, or precaution, whether or not it is considered to be associated with the study drug. A SAE is an AE that meets any of the following criteria:

- Results in death. This includes any death that occurs during the conduct of a clinical study, including deaths that appear to be completely unrelated to the study drug (e.g. car accident);
- Is life-threatening. This includes any AE during which the subject is, in the view of the Investigator, at immediate risk of death from the event as it occurs. This definition does not include events that may have caused death if they had occurred in a more severe form; Requires inpatient hospitalization or prolongation of existing hospitalization;
- Results in persistent or significant disability or incapacity;
- Is a congenital anomaly or birth defect;
- Other medical events that based upon appropriate medical judgment are thought to jeopardize the patient and/or require medical or surgical intervention to prevent one of the outcomes defining a SAE.

A Suspected Unexpected Serious Adverse Reaction (SUSAR) is a serious ADR that is unexpected or for which the development is uncommon (unexpected issue) observed during a clinical trial and for which there is a relationship with the experimental drug, whatever the tested drug or its comparator.

The drugs that may be used as standard of care in Arm B, including dexamethasone that is also used in Arm A, are investigational medicinal products (IMPs) for this study.

Section 4.8 of the relevant SmPC of each IMP used in the Study will serve as the reference safety information (RSI) for determining expectedness of serious adverse reactions (SARs) that occur with these products.

Any serious and unexpected AE that the Investigator or the Sponsor considers to be at least possibly related to study drug is subject to expedited reporting to the appropriate Health Authorities. AEs for which causality is not assessed by the Investigator are related to the study drug by the Sponsor.

## 10.2. Classification of AEs

The Investigator will classify AEs about severity and relationship to the investigational medicinal product. Every effort must be made by the Investigator to categorize each AE according to its severity and its relationship to the study drugs. If the Investigator's causality assessment is missing or unknown, the AE must be considered as related to the product.

### 10.2.1. Severity

The severity of an AE will be rated by the Investigator according to the descriptions and grading scales of the Common Terminology Criteria for Adverse Events (CTCAE) version 5, as follows:

- Grade 1 Mild; asymptomatic or mild symptoms; clinical or diagnostic observations only; intervention not indicated

CONFIDENTIAL

Confidential	MyRisk	Date: 05 February 2024
	Protocol	
	PROTOCOL NUMBER: IBA1160	Version: 5.1

- Grade 2 Moderate; minimal, local or noninvasive intervention indicated; limiting age-appropriate Instrumental Activities of Daily Living (ADL)\*
- Grade 3 Severe or medically significant but not immediately life-threatening; hospitalization or prolongation of hospitalization indicated; disabling; limiting self-care ADL\*\*
- Grade 4 Life-threatening consequences; urgent intervention indicated
- Grade 5 Death related to AE

(\*) Instrumental ADL refers to preparing meals, shopping for groceries or clothes, using the telephone, managing money, etc. (\*\*) Self-care ADL refers to bathing, dressing, and undressing, feeding self, using the toilet, taking medications, and not bedridden.

### 10.2.2. Relationship to the investigational product and/or additional study drug

For this study, a causal relationship of an AE with the study drug will be classified as either:

- RELATED
- or
- NOT RELATED

